This is a minimal risk study. Head of bed elevation is already standard of care for ventilated patients in the ICU. However, the current practice is by "eyeballing" the patient or measuring the angle of the bed rather than the patient. Aim 3 sets out to measure the actual angle of elevation of the patient and in the active phase, provide this information to the nurses to see if it can help them improve their compliance to elevation of patient's head to prevent VAP. Angulus is a non-invasive, non-significant risk device, there are not any components, which present hazardous procedures, situations or materials to personnel and/or study subjects. Moreover, intubated patients already have a number of monitors and sensors affixed on or near them during their inpatient hospitalization. An additional sensor will cause additional complications and no other monitors or sensor will be removed in order to allow Angulus to be used.

b. Sources of Materials

In Aim 1 and 3, the sources of material will be the responses from the voluntary interviews, surveys and focus group. In Aim #2, the research material obtained from human subjects will be the data sent from the Angulus sensor and stored on the iPod touch display device. This data is stored locally and does not require the input or transmission of any PHI. The iPod touch display device is securely attached below the vital sign monitor, and each disposable sensor is assigned to a specific patient and display device. Acquired data are stored in an internal database, which cannot be accessed outside the application, and advanced features such as data export are password-protected. Data export must be performed via physical connection (i.e. via USB), onto an encrypted laptop. Additional patient level data on age, gender, BMI, and race will be collected from medical records. No identifying information will be collected.

c. Potential Risks

This is ultimately a study of compliance, and even though subjects will be assigned to active or control conditions, they will still receive the same standard of care that they are receiving now, with the potential for it to improve. Given that this is a non-significant, non-invasive mechanism, we do not anticipate there to be any psychological, financial, legal risks for subjects who are enrolled in the trial. The only risk we have identified is the potential for an allergic reaction to the adhesive. To protect against this risk, we will not enroll patients with a known allergy to our adhesive.

Protection Against Risks

a. Informed Consent

For Aim 1 and 3 on the focus groups and surveys on useability of Angulus, we will apply for a verbal consent from end-users for participation. For the purpose of Aim 2, we intend to submit a request for a waiver of informed consent, as the outcomes of this trial focus exclusively on quality improvement metrics, rather than clinical efficacy outcomes. As per 45 CFR 46.116d, Aim 3 would meet the required 4 criteria for a waiver of informed consent:

- 1. The research involves no more than minimal risk to the subjects: Angulus is a non-invasive, nonsignificant risk device that aims to provide real time data to nurses and other providers on compliance to elevation of the head of ventilated patients to prevent VAP. Decision about whether to change the patient's position or bed angle is still left to the bedside clinician.
- The waiver will not adversely affect the rights and welfare of the subjects: Head of bed elevation does not require patient consent in current clinical care. Indeed, this is considered standard of care for all ventilated patients in the ICU.
- 3. The research could not be practically carried out without a waiver: Aim 2 proposes a cluster randomization of an ICU. It is neither practical nor possible to consent every ventilated patient in the ICU in a timely fashion as head of bed elevation is supposed to be implemented as soon as possible

after intubation and is part of the ventilator bundle orders for initiation of mechanical ventilation for patients at Montefiore.

4. When appropriate, the subject will be provided with additional pertinent information after participation. We do not anticipate any information from this trial will be pertinent to the patient's health or clinical outcome as elevation of head is already standard of care for patients in the ICU.

b. Protections Against Risks

To minimize the possibility of a data breach, all data will be de-identified and stored in encrypted databases to prevent the possibility for any potential breach of PHI. No names or HIPAA identifiers will be associated with computerized data files and similarly any published materials will represent de-identified aggregate data. Data collected from the sensors will be stored locally on the display device prior to being downloaded. Data will be downloaded to a secure encrypted laptop upon patient discharge.

In order to ensure strict adherence to HIPAA compliance, no data will be sent over wireless networks, and all downloaded data will be stripped of any potential patient identifiers.

In order to adhere to infection control and patient safety standards, over the course of both phases of the study, the Angulus hardware component will be enclosed in a disposable encasing with disposable adhesive. Additionally, the display devices will be encompassed in a disposable protective case to prevent the carry over of any infectious organisms during patient turnover. The only re-usable component of this mechanism is the sensor itself (which is then enclosed in a disposable encasing).

To minimize the potential for any physical adverse reactions, we will exclude any patients with a known allergy to our adhesive.

Potential Benefits

Under our current study design and hypothesis, we are proposing that implementation of the Angulus sensor with corresponding data display will improve compliance with patient HOB guidelines. This could be a potential benefit of the research to participants. Since adherence to patient elevation guidelines are currently low, and patient elevation has been shown to have a significant impact on the development of VAP, increasing compliance in this domain could greatly improve the quality of care ventilated patients are receiving.

Data and Safety Monitoring Plan

While we do not intend to establish a formal Data Safety Monitoring Board (DSMB), we will abide by local and regulatory requirements for reporting adverse events (AEs) to local and federal regulatory agencies in a timely manner. Any adverse events identified by the study team or providers will be reported to the study coordinator and both PIs, and appropriately recorded and sent to the necessary regulatory entity for review.

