Angulus will work collaboratively with our consortium-site PI, [name], at our evaluation site, Montefiore Medical Center, to implement a cluster randomized crossover trial of Angulus in human subjects.

The purpose of this trial is to determine how implementation of Angulus impacts compliance with patient elevation guidelines. *Our hypothesis is that real time feedback to nurses and bedside clinician from the Angulus sensor of the actual body angle of elevation of the patient rather than the angle of the bed can improve compliance to head elevation to 30 degrees in mechanically ventilated patients in the ICU.* In order to achieve this goal we will conduct a cluster randomized crossover study occurring in two (2) Intensive Care Units (ICU) at Montefiore Medical Center. Randomization will occur at the ICU level.

Study Population: To participate in this study a patient must meet all of the inclusion criteria and fail to meet any of the exclusion criteria.

[figure not shown]
The criteria for inclusion in this study are:

- Mechanical ventilation with any modality (e.g., endotracheal tube, tracheostomy)
- Age between 18 and 75 years

The criteria for exclusion from this study are:

- Patients with a known allergy to the encasing materials
- Patients who are advised to be positioned outside of the 30-45 degree scope.
- Patients with any major chest wall abnormalities, or defects, including but not limited to:
 - o post-cardiac surgical patients
 - o pectus excavatum (or any congenital chest wall deformity)
 - o complicated skin and soft tissue infections on the chest wall
 - o heart-lung machine systems

Study Design: This is a two arm, clustered randomized cross over trial looking to see whether feedback from the Angulus device will promote greater compliance to patient elevation in the ICU. The overall study design is see in Figure 4.

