After receiving full IRB approval, all ICU nurses will receive didactic training on VAP, the importance of head-of-bed elevation, and a refresher on best-practice guidelines for implementing and ensuring compliance with the VAP bundle. These trainings will take place on two (2) separate occasions before each period to ensure that all ICU nurses receive the training, and will incorporate an evaluation component to assess comprehension. During each period, research coordinator will screen each unit for newly intubated patients who fulfill the inclusion criteria but none of the exclusion criteria. Eligible patients in the study ICUs at all periods will be equipped with the Angulus Device by tape to their sternum. Each potential participant will be given a de-identified patient code. Subjects will be enrolled in the trial within 36 hours of intubation, and will remain in the trial until discharge from Note that the Angulus is placed externally on the patient's chest and secured with the ICU. adhesives similar to what is used for EKG leads used clinically in the ICU. Angulus' only function is to measure the angle of elevation of the patient in their current position. For further discussion on the protection of human subjects, please see the human subjects section. The Angulus device will be collecting data on patient elevation "in the background." This will allow us to quantify the extent to which compliance with patient elevation is compromised under existing workflow limitations.

During Period 1, each ICU will be randomized to Feedback of No Feedback. The ICU with feedback will be equipped with display device (ipod) corresponding to each Angulus device with an

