interactive software interface which displays the patient's elevation and sends a color-coded cue when patients fall outside of the desired patient elevation scope. Nurses will be able to set up the display device and utilize all of its functionality including a snooze feature, which allows providers to pause the cue when patients are having a procedure, which requires they be positioned outside of the desired recumbent scope (i.e. a chest x-ray, etc.), or if the device must be removed (i.e. for bathing). Having the Angulus sensor with the corresponding display device will allow nurses to intelligibly and efficiently understand a patient's elevation and make corrections as needed throughout their workday. Nurses can decide to use this information to reposition the patients to reach the target elevation. In ICUs that are randomized to NO Feedback in Period 1, the Angulus device not have a corresponding display device and the data on patient elevation will NOT be displayed to the nurses. Nurses will continue to operate under existing clinical practices for compliance with hospital practice for elevation > 30 degrees, checking patient elevation according to existing methods. In Period 2, each ICU will cross over to the other arm and in Period 3, they will cross over back to the original arm. Three ICU (Moses MICU, Moses SICU, Weiler MSICU) will be randomized as cluster with all patients who are mechanically ventilated in those ICU randomized as a cluster to Feedback or No Feedback. During all periods of the study, whether the bedside clinician/nurse decides to adjust the patient's body position or bed is left up to their clinical judgement.

Statistical Analysis:

The primary outcome is compliance to head of bed elevation to 30 degree or more. This will be measured as a continuous variable between 0% and 100% compliance. This is defined as: Compliance= 100 x ((Total time in minutes in which patients in ICU are elevated > 30 degree during period) / (Total time patients in ICU spent with Angulus device during period))

From an inferential point of view, our goal is to use the data collected by the Angulus sensor to evaluate the effect that real-time feedback mechanism has on improving compliance with patient elevation guidelines. Indeed, by automating the data collection pipeline, our study will gather patient levels with more ease and at a finer temporal scale than was previously possible. Secondary outcomes of interest include:

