- Frequency that patients in the ICU are rotated more than 30 degree within 24 hour days and association with development of decubitus ulcers. As the technology in Angulus measures movement in 3 dimensions, it automatically records rotation in addition to elevation of patients. Another best care measure for mechanically ventilated patients is regular turning of patients to prevent formation of decubitus ulcers. This analysis will explore whether frequency of rotation for a patient is associated with subsequent development of decubitus ulcers. In this analysis, patients from all period and ICUs will be combined but the analysis will be stratified by period and ICU.
- Frequency that patients in the ICU rotate more than 30 degree and have change in elevation of more than 15 degree within an hour and correlation with agitation as indicated by RASS.
 Frequent movement in patients on the ventilator can indicate agitation. RASS is a clinically collected parameter indicative of levels of consciousness and agitation.

Montefiore has 3 MICUs and all of the Montefiore ICU units has 12-16 beds. Based upon preliminary work, there are an average of 25 patients who are newly intubated each month within each ICU and the average duration of mechanical ventilation is 3 days. That translate to about 75 patient-vent days per month. Table 2 shows detectable difference given this expected sample size at different powers. We aim to conduct the study in 3 ICU over 3 months total.

Table 2. Sample Size needed based on the minimal detectable difference for mean time in range between the monitored group and the non-monitored group

	70%	75 %	80%	85%
--	-----	------	-----	-----

	Power	Power	Power	Power
Detectable Difference				
10% difference in means	80	94	100	120
15% difference in means	38	42	48	56
20% Difference in means	20	24	26	30
25% Difference in means	14	16	18	20

Aim 4: Integrate critical end-user functionality post-implementation with an agile and iterative product development approach and assess end-user satisfaction and usability scores.

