a. Human Subjects Involvement, Characteristics and Design

Angulus, as a product, has been developed specifically to improve compliance with patient elevation guidelines for ventilated patients in the ICU.

Aim 1 and 3 involves focus groups and surveys/questionaires of ICU care providers and hospital leaders in hospital safety and quality control who are often concerned about measuring, preventing and reporting VAP in the hospital. This will be conducted at Montefiore Medical Center and will involve anonymous participation from the respondents in which they will be queried about features and functionality of Angulus to help guide refinement of the product. No personal information or identifiers of the participants will be collected. We plan on a verbal consent from participants.

Aim 2 outlines a cluster cross over randomized clinical trial designed to evaluate the usefulness and feasibility of Angulus in a critical care setting. We will enroll ventilated patients from 3 ICUs in this trial. We anticipate that study participants will be older than 18, have an equal male to female ratio, and have poor health status. Randomization will occur at the unit-level, not the individual level, and each unit will serve as its

own control as with our current study design the assignments switch after each period. We will apply for a waiver of informed consent for data collection as this study fulfills all criteria for waiver of informed consent:

Subjects will be enrolled in the trial within 36 hours of intubation, and will remain in the trial until ICU discharge.

Participation is not limited by patients' race, sex, ethnicity or socioeconomic class, and no potential subjects will be excluded based on these criterion. We are not incorporating fetuses, neonates, pregnant women, children, prisoners or institutionalized individuals, although ventilated patients are considered to be a vulnerable population.

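### The primary compliance ratio is not limited to ventilated minutes, so any device time after extubation counts towards an endpoint meant for mechanically ventilated patients

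*Combined protocol and SAP*

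**What the plan says.** **Endpoint.** The Statistical Analysis section of Aim 2 defines compliance as 100 times the minutes in which ICU patients are above 30 degrees during the period, divided by "Total time patients in ICU spent with Angulus device during period". Ventilation appears in neither term.

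**Follow-up.** Ventilation is an inclusion criterion, so it applies at entry. The Human Subjects Involvement section then states: "Subjects will be enrolled in the trial within 36 hours of intubation, and will remain in the trial until ICU discharge". The Study Design text says the same ("and will remain in the trial until discharge from" the ICU; the sentence is broken by the page layout). Under Protections Against Risks, sensor data are downloaded when the patient is discharged. No section removes the sensor, stops recording or censors minutes at extubation. None says that the sensor stays on, either.

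**Question and planned exposure.** The Aim 2 hypothesis is that feedback can "improve compliance to head elevation to 30 degrees in mechanically ventilated patients in the ICU". Exposure is counted in ventilated time only: 25 newly intubated patients per ICU per month, ventilated 3 days on average. "That translate to about 75 patient-vent days per month". One sentence under Study Design is broader: feedback is to "promote greater compliance to patient elevation in the ICU".

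**The concern.** The endpoint and the hypothesis may cover different time. Specific Aims and the human-subjects sections describe the elevation standard for ventilated patients. The documents state no elevation standard for an extubated patient, so compliance in those minutes has no stated reference.

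Two things are at stake:

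- **Dilution.** If feedback changes positioning less after extubation, those minutes pull the measured difference below the effect named in the hypothesis. Phase I feasibility is judged partly on a 15% improvement in compliance, so the denominator can affect that decision.
- **Imbalance.** If the post-extubation share of device time differs between arms, the ratio can move even when feedback does nothing. With no rule for when the sensor comes off, equal shares are not assured.

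**Working it through.** **1. The plan's own exposure figure.** 25 patients x 3 ventilated days = 75 patient-ventilator days per ICU-month, as stated. This is ventilated time only. As the ratio is written, device time counted from intubation would be 25 x (3 + k), where k is the mean number of post-extubation device days. The documents do not give k. For k = 0, 1, 2, 3 the result is 75, 100, 125, 150 device days per ICU-month.

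**2. Dilution formula.** Let V be ventilated device days, k post-extubation device days, s = k/(V + k) the post-extubation share of device time, and f the fraction of the effect that persists after extubation.

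Measured effect = 15 x (1 - s x (1 - f))

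Inputs from the documents:
- Average ventilation is 3 days (sample-size text).
- Enrolment is 0 to 36 hours after intubation. V for an average patient is therefore between 3 days and 72 h - 36 h = 36 h = 1.5 days.

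Assumptions:
- The effect during ventilation is 15 percentage points, chosen to match the 15% success criterion.
- s is the same in both arms.
- k runs from 0 to 3 days.
- f is 0, 0.5 or 1.

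| V (days) | k (days) | s | f = 0 | f = 0.5 | f = 1 |
|---|---|---|---|---|---|
| 3 or 1.5 | 0 | 0% | 15 | 15 | 15 |
| 3 | 1 | 25% | 11.25 | 13.1 | 15 |
| 3 | 2 | 40% | 9.0 | 12.0 | 15 |
| 3 | 3 | 50% | 7.5 | 11.25 | 15 |
| 1.5 | 1 | 40% | 9.0 | 12.0 | 15 |
| 1.5 | 2 | 57% | 6.4 | 10.7 | 15 |
| 1.5 | 3 | 67% | 5.0 | 10.0 | 15 |

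Example (V = 3, k = 1, f = 0.5): s = 1/4, so 15 x (1 - 0.25 x 0.5) = 13.1.

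**3. Unequal shares with no feedback effect.** Assume ventilated compliance of 50% in both arms, and post-extubation shares of 25% with feedback and 40% without.
- Post-extubation compliance 30%: 0.75 x 50 + 0.25 x 30 = 45.0 against 0.60 x 50 + 0.40 x 30 = 42.0, a spurious +3.0 points.
- Post-extubation compliance 80%: 0.75 x 50 + 0.25 x 80 = 57.5 against 0.60 x 50 + 0.40 x 80 = 62.0, a spurious -4.5 points.

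These shares and levels are illustrations; the documents give none of them.

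**The case against.** The best defence is that the authors meant ventilated time throughout. The cluster is described as "all patients who are mechanically ventilated in those ICU randomized as a cluster to Feedback or No Feedback", exposure is counted in ventilator days, and the documents seem to use ICU patients as shorthand for ventilated ones. For example, the rotation outcome is worded "Frequency that patients in the ICU are rotated more than 30 degree within 24 hour days", but its rationale refers to mechanically ventilated patients. Remaining in the trial is also follow-up, not an instruction to keep the sensor taped on. On this view a clarifying sentence is enough.

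Part of this stands. Post-extubation wear is not shown, and the rotation outcome is no real evidence for it. The lowest figures are corner cases: 5.0 points needs enrolment at the 36-hour limit, three further device days and no effect at all after extubation. If sensors stay on, the display and its cue carry no ventilation condition, so feedback would probably continue and f = 0 may be too severe. All-device time is also a legitimate quantity under the broader Study Design sentence.

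It does not remove the problem. The cluster description selects patients, not minutes. The ratio is an explicit rule that counts all device time, and the follow-up and download statements run to discharge with no earlier stop. If two readings are possible, the plan has not said which is primary.

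**Conclusion.** The concern holds. As written, the primary ratio admits minutes outside the stated hypothesis whenever the sensor is worn after extubation. That conclusion rests on the text and needs none of the figures above.

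The size of the effect cannot be determined from the documents. Under the stated assumptions a 15-point effect during ventilation is measured as anything from 15 points (no post-extubation wear, or an unchanged effect) down to 7.5 points with 3 ventilated device days, or 5.0 at the 36-hour enrolment limit. If half the effect persists, the range is 15 down to 10.0. The sponsor should correct this before analysis; it does not call the design itself into question.

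**What to change.** Define numerator and denominator as minutes within the period when the patient is on mechanical ventilation, the sensor is worn and an angle is recorded. Abstract the start and stop times of every ventilation episode, including reintubation and repeated episodes in tracheostomy patients. Report the all-device-time ratio as a secondary outcome, with the percentage of device time that was ventilated in each arm, so that readers can see whether the restriction matters. If the sponsor prefers all device time as primary, the hypothesis and planned exposure should be restated to match, with ventilated time as a sensitivity analysis.

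Cost: endpoint wording and chart abstraction for at most about 25 x 3 ICUs x 3 months = 225 patients, before the age and chest-wall criteria are applied. Intubation time is already needed for the 36-hour window, so the addition is mainly stop times and later episodes; intermittent ventilation takes more work. The chart data listed under Sources of Materials (age, gender, BMI, race) would need a small extension, and the times must fit the plan's de-identification commitments. The agitation and ulcer outcomes already need data beyond that list. There will be fewer minutes per patient but no fewer patients.

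### No primary test or model is stated for the three-period cluster crossover, with no ICU term, period term or handling of clustering; the only comparison described is an unclustered two-group difference

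*Combined protocol and SAP*

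**What the plan says.** - **Outcome.** Aim 2, Statistical Analysis, defines compliance as a ratio of minutes summed over the patients in an ICU during a period. That is one value per ICU and period: nine with three ICUs, six with two.
- **Analysis.** The same section then says only that "our goal is to use the data collected by the Angulus sensor to evaluate the effect that real-time feedback mechanism has on improving compliance". No test, model, variance method, significance level, ICU term or period term follows.
- **The only comparison described.** Table 2 is captioned as a difference in "mean time in range between the monitored group and the non-monitored group".
- **Schedule.** "During Period 1, each ICU will be randomized to Feedback of No Feedback". "In Period 2, each ICU will cross over to the other arm and in Period 3, they will cross over back" to where they started. Each ICU therefore follows Feedback-No Feedback-Feedback (FNF) or the mirror (NFN).
- **Design rationale.** The Human Subjects section calls each unit its "own control as with our current study design the assignments switch after each period", but attaches no analysis to this.
- **ICU and period as strata.** "the analysis will be stratified by period and ICU" is written for the secondary rotation and decubitus ulcer analysis only.
- **Number of ICUs.** Two in Specific Aims and at the start of Aim 2; three in Study Design, the sample-size paragraph and Human Subjects.
- **Success criterion.** Phase I Success Criteria asks for a 15% improvement in compliance, together with no device-related adverse events.

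**The concern.** ICUs are randomised and each changes arm over time. The analysis therefore has to deal with patients clustered within ICU-periods, and with ICUs and periods that are not shared equally between arms. The plan leaves both open.

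The natural default, a two-sample comparison of patients as in Table 2, treats patients as independent, so its p-value and interval would claim more certainty than the design gives. A pooled contrast also carries ICU and period differences into the estimate, because every ICU contributes 2:1 to the arms and three ICUs cannot be split evenly between two sequences. With nothing pre-specified, the contrast could be chosen after the data are seen, and its estimate is then compared with the 15% criterion.

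**Working it through.** **Inputs from the documents.** Three ICUs and three periods; sequences FNF or NFN; an average of 25 newly intubated patients per ICU per month; the 16 entries of Table 2; the 15% criterion.

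**Assumptions not in the documents.** ICC 0.01 to 0.10; between-period correlation r of 0.8 to 0.5; one-month periods, hence 25 patients per ICU-period (not reduced for eligibility); equal cells; a 10-point ICU or period gap for illustration; 15% read as percentage points.

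**1. Table 2.** SD, alpha, sidedness and total or per-arm N are not given, so the table cannot be reproduced from stated inputs. The SD can be back-solved. For an ordinary two-sample comparison (normal approximation, two-sided 5%, N as total), n per arm = 2(1.960 + 0.842)² SD²/d². With SD 18.25, d = 15 and 80% power this is 23.2, so 24 per arm and 48 in total, as in the plan. The same SD gives 11 of the 16 entries exactly; the other five differ by 2 to 6. Solving each entry with a t-test gives SD 17.0-18.4 if N is total and 24.8-26.3 if per arm; 18 and 25 are used below. Several variants fit about equally well, and all are unclustered.

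**2. Contrast weights, three ICUs split 2:1 (FNF, FNF, NFN).** There are five Feedback cells (+1/5 each) and four No Feedback cells (-1/4 each).
- FNF ICU: 2/5 - 1/4 = +0.15. NFN ICU: 1/5 - 2/4 = -0.30.
- Periods 1 and 3: 2/5 - 1/4 = +0.15 each. Period 2: 1/5 - 2/4 = -0.30.
- Signs reverse in the mirror allocation. A linear trend cancels (+0.15 × 1 - 0.30 × 2 + 0.15 × 3 = 0), so period matters only if Period 2 departs from the mean of Periods 1 and 3.

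An own-control contrast (Feedback minus No Feedback within each ICU, then averaged) has ICU weights of 0 but period weights of +0.167, -0.333, +0.167. With two ICUs split 1:1, the pooled weights are ±0.333 by ICU and 0 by period.

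**3. Effect on the estimate.** With both sequences used there are six equally likely allocations. If one ICU differs by 10 points, the pooled estimate moves 10 × 0.15 = 1.5 points in the four where that ICU is not alone and 10 × 0.30 = 3 points in the two where it is. Root mean square: √[(4 × 1.5² + 2 × 3²)/6] = 2.1. A 10-point shift in Period 2 alone moves the pooled estimate 3.0 points and the own-control estimate 3.3. A model with ICU and period terms moves in neither case.

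**4. Type I error of a pooled patient-level t-test.** In units of SD², the variance it assumes is 1/125 + 1/100 = 0.018. The actual variance is 0.135 × r × ICC + 0.45 × (1 - r) × ICC + 0.45 × (1 - ICC)/25, where 0.135 = 0.15² + 0.15² + 0.30² and 0.45 = 1/5 + 1/4. At ICC 0.05 and r = 0.8 this is 0.0054 + 0.0045 + 0.0171 = 0.0270. The true critical value is 1.971 × √(0.018/0.027) = 1.61, an error of 10.8%.

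| ICC | Formula, r = 0.8 to 0.5 | Simulation, 20,000 null trials |
|---|---|---|
| 0.01 | 6.0-6.6% | 6-7% |
| 0.05 | 10.8-13.8% | 11-14% |
| 0.10 | 16.3-21.5% | 17-23% |

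A pooled t-test on the nine ICU-period values is conservative (2-5%). The ICU + period + Feedback model on those values holds about 5%.

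**5. The adjusted model.** With a 2:1 split the design matrix has full rank 6, leaving 9 - 6 = 3 residual df, and Var(Feedback) = 0.5625 × the cell variance (0.45 pooled, 0.50 own-control). At SD 18, ICC 0.01 and r = 0.8 the cell variance is 324 × (0.002 + 0.0396) = 13.5 and the SE is √(0.5625 × 13.5) = 2.75. The mean 95% half-width is 3.18 × 2.75 × 0.921 = 8.1 points, where 0.921 is the mean of the estimated over the true SE at 3 df. At ICC 0.10 and r = 0.5 it is 11.6. At SD 25 the range is 11.2-16.1. The patient-level test would report about 4.8 (SD 18) or 6.6 (SD 25).

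If all three ICUs drew the same sequence, the rank would be 5 of 6 and Feedback could not be separated from period.

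**The case against.** - **The unit is partly given.** The outcome formula yields ICU-period values, and a simple t-test on those would not inflate the error. This stands. A reader might infer that the plan commits to a patient-level test, or that no unit can be found in it. Neither is supported: Table 2 is a sample-size table, not an analysis statement. But the outcome definition and Table 2 point to different units, and nothing chooses between them.
- **The imbalance is not a bias.** The weights average zero over randomisation. A reader might infer that the choice of contrast will usually decide whether 15% is reached. The documents give no between-ICU data to support that. At SD 18, ICC 0.05 and r = 0.8 the pooled and adjusted estimates both have SD √(0.027 × 324) = 2.96, and with a true gain of 12 each reaches 15 about 16% of the time. The shift matters only when an ICU or Period 2 happens to differ markedly.
- **The success criterion has no significance threshold.** True, so type I error does not enter the feasibility decision. It does affect any p-value or interval reported for Aim 2.
- **Randomisation may already be restricted.** The reference to "In ICUs that are randomized to NO Feedback in Period 1" beside an ICU with feedback suggests both arms in Period 1, and "The overall study design is see in Figure 4" points to a figure not available here. One cannot infer that randomisation is unrestricted, only that the available text does not state a restriction.
- **Patients may straddle a crossover.** They stay enrolled until ICU discharge, so some may contribute to two periods. The calculations ignore this and any carryover.

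**Conclusion.** The concern holds: the plan names a primary outcome but no primary analysis, and the one comparison it describes ignores the clusters and periods of its own design. That gap depends on none of the assumed values.

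Its size does. A patient-level test at a nominal 5% would run at about 6-7%, 11-14% or 17-23% for ICC 0.01, 0.05 or 0.10, given r of 0.8 to 0.5 and 25 patients per ICU-period. At r = 0 the formula gives 8%, 18% and 29%. With three ICUs split 2:1, an assumed 10-point ICU gap moves a pooled estimate by 1.5 or 3 points in either direction. The case for change rests on valid intervals and a fixed choice of contrast, not on systematic bias. It should be settled before Period 1.

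**What to change.** 1. Reconcile the number of ICUs, because the residual df depend on it.
2. State that randomisation is restricted so both sequences are used. With three ICUs, draw at random which ICU is alone and which sequence it gets.
3. Pre-specify one primary analysis: a linear model on the ICU-period compliance values already defined, with ICU, period and Feedback effects, reporting the Feedback estimate and 95% CI on t with 3 df (three ICUs). Any patient-level mixed model should be a sensitivity analysis only; unless weighted by minutes, it estimates a mean of patient percentages rather than the plan's time-weighted ratio.
4. Apply the 15% criterion to that Feedback estimate, and say whether it means percentage points.

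**Cost.** Analysis wording and a restricted randomisation list; no extra patients. The price is precision: the mean half-widths of about 8-12 points (SD 18) or 11-16 (SD 25) go with power of 71-94% or 47-74% for a 15-point difference. If monitored time varies strongly between patients (coefficient of variation 1, assumed), the half-widths become 11-14 or 15-19 points. With two ICUs only 1 residual df remains; even at SD 18, ICC 0.01 and r = 0.8 the mean half-width is 12.71 × √(0.75 × 13.5) × 0.798 = 32 points, so the ICU count should be settled with this in view.
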